#### **4.1 Overall Research Design:**

This research plan proposes experiments that are critical to advance our understanding of glutamatergic signaling in alcohol use disorders. We will recruit moderate drinkers and Alcohol Use Disorder subjects between the ages of 21 to 55 years to participate in the recruitment, evaluation, and imaging. Moderate drinkers are defined as people who report consuming alcohol on at least one occasion in the past three months that would result in an estimated blood alcohol level greater than 80 mg/dl but not meet DSM-5 criteria for AUD. This is operationally defined as more than 3 standard drinks in a single occasion for women and 4 standard drinks in a single occasion for men. All participating subjects will be seen for an initial intake, including a full physical exam and medical coding. Thereafter, they will have an anatomical MRI scan, followed by a series of [C]ABP688 and/or [F]FPEB PET scans with alcohol challenge as described in the below aims:

**Aim 1** will evaluate the sensitivity of the mGlu5 radioligand [F]FPEB to alcohol release in the same subjects (moderate drinkers,  $n=10$ ). Subjects will participate in up to two [F]FPEB scans with alcohol challenge that measure mGlu5 availability under the following conditions: baseline and 60 mg/dL alcohol administration. This will be conducted with the following sub-aims:

**Aim 1a** will administer the alcohol (targeting 60 mg/dL) as an oral challenge. This will be done in at least the first 5 subjects. At this point, the percent change in mGlu5 receptor availability (i.e., [F]FPEB  $V_T$ ) will be evaluated. If this remains within test-retest estimates of this radiotracer (9-12%) {Park, 2015 #219} in subjects achieving the targeted alcohol dose, then we may proceed to Aim 1b:

**Aim 1b** will administer the alcohol (targeting 60 mg/dL) as an i.v. challenge.

**Aim 2** will evaluate the sensitivity of the mGlu5 radioligand [C]ABP688 to alcohol release in the same subjects (moderate drinkers,  $n=10$ ). Subjects will participate in up to two [C]ABP688 scans with alcohol challenge that measure mGlu5 availability under the following conditions: baseline and 60 mg/dL alcohol administration. This will be conducted with the following sub-aims:

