#### Breakdown of Aims 1-3

- Aim 1: 10 moderate drinkers
- Aim 2: 10 moderate drinkers

- Aim 3: 30 moderate drinkers (minus drinkers from chosen tracer in Aim 1 or 2), and 30 AUD

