MR image. The T1-weighted MR image will be non-linearly registered to MNI space for region of interest (ROI) identification. ROIs will be selected using the Anatomical Automatic Labeling template for SPM8. To minimize possible partial volume effects, only gray-matter voxels will be included in ROI definition based on MRI segmentations performed with the Computational Anatomy Toolbox. Since glutamate release has been observed throughout the brain, ROI analyses will focus on the primary brain regions of frontal, parietal, temporal, and occipital cortices; striatum, amygdala, hippocampus, thalamus, and cerebellum. The primary outcome measure will be [C]ABP688 or [F]FPEB  $V_T$  estimated with the 2-tissue compartment model as previously validated, which yields a test-retest variability of <12%.

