**7. Plan for reporting adverse events:**

For the current study, the following individuals, funding, and/or regulatory agencies will be notified (choose those that apply):

- All Co-Investigators listed on the protocol.
- National Institutes of Health
- Yale University Radioactive Drug Research Committee (if applicable)
- Yale University Radiation Safety Committee (if applicable)

The principal investigator, [name], in collaboration with [name] will conduct a review of all adverse events upon completion of every study subject. The principal investigator will evaluate the frequency and severity of the adverse events and determine if modifications to the protocol or consent form are required.

d. For multi-site studies for which the Yale PI serves as the lead investigator: **N/A**

- i. How will adverse events and unanticipated problems involving risks to subjects or others be reported, reviewed and managed?
- ii. What provisions are in place for management of interim results?
- iii. What will the multi-site process be for protocol modifications?

d. For multi-site studies for which the Yale PI serves as the lead investigator:

- iv. How will adverse events and unanticipated problems involving risks to subjects or others be reported, reviewed and managed? *Write here*
- v. What provisions are in place for management of interim results? *Write here*
- vi. What will the multi-site process be for protocol modifications? *Write here*

**13. Statistical Considerations:** Describe the statistical analyses that support the study design.

Frequency distributions and descriptive statistics for all variables will be computed before conducting analyses. Should Shapiro-Wilk normality tests indicate non-normality for any continuous variable, we will compute necessary data transformations (e.g., logarithmic) before conducting analyses.

**AIMs 1 and 2:** To determine which radiotracer is most sensitive to alcohol's effects on glutamate, regional  $V_T$  values (estimated for each radiotracer) will be analyzed with a linear mixed model featuring scan state (baseline and post-alcohol) as within-subject fixed factors, and region as a within-subjects factor. We hypothesize that the model will identify a significant main effect of scan state. Planned post-hoc contrasts will examine regional differences in  $V_T$  by scan state.

Effect sizes of alcohol relative to baseline will also be estimated. These values will guide selection of the experimental protocol for Aim 3.

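### The Aims 1-2 mixed model does not say what scan state is tested against; if subject-by-scan-state variation is left out, the test is in most plausible settings too liberal

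*Combined protocol and SAP*

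**What the plan says.** Section 13 (Statistical Considerations), AIMs 1 and 2, has regional V_T analysed with a "linear mixed model featuring scan state (baseline and post-alcohol) as within-subject fixed factors, and region as a within-subjects factor". The one inferential prediction is: "We hypothesize that the model will identify a significant main effect of scan state". Post-hoc contrasts by region follow. Effect sizes of alcohol against baseline are also to be estimated, and these guide the choice of protocol for Aim 3. Random effects, residual covariance, degrees-of-freedom method, significance level and sidedness are not given here or elsewhere.

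The section on PET data acquisition and analysis lists nine regions: "frontal, parietal, temporal, and occipital cortices; striatum, amygdala, hippocampus, thalamus, and cerebellum". V_T comes from a two-tissue compartment model, "which yields a test-retest variability of <12" percent. The breakdown of aims gives the sample sizes: "Aim 1: 10 moderate drinkers" and "Aim 2: 10 moderate drinkers". In section 4.1 the oral challenge comes first ("This will be done in at least the first 5 subjects"). The switch to i.v. is then judged by comparing percent change with test-retest estimates, not by this model.

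**The concern.** Each subject contributes two scans and nine regions, 18 values in all. The regions of one scan are not separate experiments. They share one injection, one arterial input and one metabolite correction, and they also share that person's response to alcohol. The plan itself expects response to differ between people, since it relates change in V_T to subjective effects. All of this is subject-by-scan-state variation, and it is what the average alcohol effect has to be judged against.

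A model with only the two listed factors and a subject intercept estimates its error from a pooled residual, in which this variation is diluted. Ten within-subject changes (9 df) are then treated as if they carried far more information. At stake is the only hypothesis test stated for Aims 1 and 2, with its interval.

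**Working it through.** The plan states no error rate or power for Aims 1-2, so there is no figure to reproduce. The check asks what happens under no alcohol effect with different error terms.

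**Inputs from the documents:** n = 10 subjects, R = 9 regions, 2 scans.

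**Assumed, because not stated:** two-sided 5%; the split of scan-to-scan change into a part shared by all regions and a region-specific part; the subject-by-region SD. The test-retest figures (9-12% and below 12%) describe total variability and do not give the split.

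**Notation.** ρ = shared variance / (shared + region-specific variance). τ² = subject-by-region variance divided by the total scan error variance of one scan, which is half the variance of change.

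**Degrees of freedom.** Intercept only: (10 − 1) × (18 − 1) = 153. Intercept plus subject-by-region: (10 − 1) × 9 = 81. Per-subject mean changes: 10 − 1 = 9.

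**True variance of the mean change divided by the variance the model assumes** (balanced data):
- Intercept only: (1 + 8ρ) / (1 − 8ρ/17 + 16τ²/17)
- Intercept plus subject-by-region: 1 + 8ρ
- Tested against per-subject mean change: 1

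The approximate false-positive rate is 2 × [1 − Φ(1.96/√ratio)].

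**Worked case, 8% shared and 6% region-specific.** ρ = 64/100 = 0.64.
- Intercept only, τ = 0: 6.12/0.699 = 8.76. The standard error is too small by √8.76 = 2.96; 1.96/2.96 = 0.66; rate 51%.
- Intercept only, subject-by-region SD 10%: τ² = 100/50 = 2; 6.12/(0.699 + 1.882) = 2.37; √2.37 = 1.54; 1.96/1.54 = 1.27; rate 20%.
- Intercept plus subject-by-region: ratio 6.12; √6.12 = 2.47; 1.96/2.47 = 0.79; rate 43%.

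**All four splits, log V_T:**

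| Shared / region-specific SD | ρ | Intercept only, τ = 0 | Intercept only, subject-by-region SD 10% | Intercept + subject-by-region | t test on subject mean change |
|---|---|---|---|---|---|
| 10% / 4% | 0.86 | 59% | 30% | 49% | 5% |
| 8% / 6% | 0.64 | 51% | 20% | 43% | 5% |
| 6% / 8% | 0.36 | 36% | 10% | 32% | 5% |
| 4% / 9% | 0.16 | 22% | 3% | 20% | 5% |

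Simulation with 20,000 null data sets per cell agrees to within about one percentage point. On a ρ grid from 0 to 0.9, rates at n = 5 were nearly the same as at n = 10.

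**When it is not liberal.** Setting the intercept-only ratio to 1 gives ρ = τ²/9; below that the test is conservative. In the last row τ² = 100/48.5 = 2.06 and τ²/9 = 0.23, above ρ = 0.16, hence 3%. At ρ = 0 and τ = 1 the simulated rate was 0.8%.

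**Untransformed V_T.** Section 13 transforms only if normality fails. With an assumed three-fold regional range, intercept-only rates were 38%, 31% and 8% for 10/4, 8/6 and 4/9. A repeat simulation gave 9 to 42% over the splits.

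**Regional contrasts.** In the intercept-only model with τ = 0 and ρ = 0.5, the variance ratio for the change in one region is 1/(1 − 4/17) = 1.31 (too liberal). For a difference in change between two regions it is 0.5/0.765 = 0.65 (too conservative).

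**Degrees of freedom matter too.** With the subject-by-scan-state term included but tested by a Wald z, the rate was still about 10% (150 fits each at ρ = 0.5 and 0.75).

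**The case against.** A reader might infer that the plan has chosen the wrong error term. The text does not support that. It names a model class and two within-subject factors and is silent on the rest. It can be read as a conventional repeated-measures analysis, in which a within-subject factor is tested against its interaction with subject on 9 df. That objection stands, so the inflation is conditional on how the model is fitted. A fully unstructured covariance would also cover the problem, but 18 × 19/2 = 171 parameters cannot be estimated from 10 subjects, so some structure has to be chosen and should be named.

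A reader might also infer that the test is always far too liberal. It is not. The size depends on ρ and on subject-by-region variance, neither of which the documents give, and the intercept-only model can be conservative.

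Third, a reader might infer that the tracer or route would be chosen wrongly. The route rule uses percent change against test-retest estimates, and the Aim 3 choice uses effect sizes. In balanced data the mean change is the same whichever error term is used. What remains is narrower: the plan does not define effect size, and one standardised by the model's residual SD, or shown with a model-based interval, would carry the wrong error term. The distortion depends on ρ, which may differ between tracers.

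**Conclusion.** The point holds as a conditional one. The error structure for the scan-state test is unspecified, and the most literal fits (subject intercept, with or without subject-by-region) give false-positive rates mostly between about 10 and 60% at a nominal 5%. Adding subject-by-region alone does not cure this: rates stay at 20 to 49% over the four splits. The exception is the intercept-only model with small shared error and large subject-by-region variance, which is near or below nominal.

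The figures rest on an assumed two-sided 5% level, balanced data and assumed splits of error. The results exposed are the scan-state test, its intervals, the regional contrasts (in either direction) and any model-standardised effect size. Because the direction depends on quantities not known in advance, the structure should be fixed before the data are seen. This is more than a missing detail, since the stated hypothesis test of Aims 1-2 depends on it.

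**What to change.** In section 13, AIMs 1 and 2, state that scan state is tested against between-subject variation in change, by one of:
- a mixed model with random effects for subject, subject-by-scan-state and subject-by-region, with Kenward-Roger degrees of freedom; or
- a one-sample t test on each subject's mean change over the nine regions, with n − 1 df, which is equivalent in balanced data.

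Build the regional contrasts, intervals and effect sizes on the same per-subject changes, and state the significance level and sidedness. Subject-by-region should be included. Without it, in a simulation with subject-by-region SD equal to the total scan-error SD and degrees of freedom approximating Kenward-Roger, the subject-by-scan-state variance was estimated as zero in 96%, 60% and 19% of data sets at ρ = 0, 0.1 and 0.25. The test then rejected in 0.6%, 3.0% and 4.6%.

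The change needs a sentence or two and no extra subjects or scans. The downside is wider intervals and less favourable p values than an intercept-only model would usually show.

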**In Aim 2 we will determine the sensitivity of the PET radioligand [C]ABP688 to the glutamate response from a fixed-dose alcohol session.** [C]ABP688  $V_T$ , an index of the number of mGlu5 available for radioligand binding, will be estimated throughout the brain. We hypothesize that alcohol will significantly reduce [C]ABP688  $V_T$  in the prefrontal cortex and striatum compared to baseline, consistent with glutamate release. The prefrontal cortex and striatum are brain regions with reported alcohol-induced glutamate release in preclinical models.

The route of alcohol administration has important effects on brain neurochemistry. While oral alcohol provides a more naturalistic route of administration, the effects of first pass metabolism and gut absorption result in slower acute brain effects, which neuroimaging studies are typically less sensitive to. Therefore, the research plan will first evaluate the glutamate response to acute oral alcohol. However, given the diminished sensitivity of neuroimaging to this route of administration, should no effects of oral alcohol on brain neurochemistry be detected, we then plan to test for sensitivity to i.v. alcohol to leverage the more potent acute effects. This question of route of administration is a critical question in the experimental paradigm optimization, and will be addressed in subaims 1A, 1B, and 2A, 2B, respectively, before continuing to Aim 3.

Based on the results of the first aims, we will identify an optimal experimental paradigm. Using this approach, we next will recruit 30 moderate drinkers and 30 people who meet DSM-5 criteria for alcohol use disorder. Subjects will self-report recent and lifetime drinking patterns. Alcohol-induced glutamate release will be measured with ONE of the experimental approaches identified above to accomplish the following aim:

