**Aim 2a** will administer the alcohol (targeting 60 mg/dL) as an oral challenge. This will be done in at least the first 5 subjects. At this point, the percent change in mGlu5 receptor availability (i.e., [C]ABP688  $V_T$ ) will be evaluated. If this remain within test-retest estimates of this radiotracer (<12%) in subjects achieving the targeted alcohol dose, then we may proceed to Aim 2b:

**Aim 2b** will administer the alcohol (targeting 60 mg/dL) as an i.v. challenge.

We will strive to recruit the same subjects from Aim 1 for Aim 2, in order to directly compare the two experimental approaches in the same people.

The results of these two aims will inform the selection of an optimal experimental design.

**Aim 3** will compare the alcohol-induced glutamate release in moderate drinkers ( $n=30$ , including subjects from the chosen tracer from Aim 1 or 2) and individuals with alcohol use disorder ( $n=30$ ). Subjects will participate in up to two mGlu5 scans under the following conditions: baseline and 60 mg/dl alcohol administration.

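### If the oral-to-i.v. switch is used, the Aims 1 and 2 model averages the alcohol effect over routes and cannot answer the route question

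*Combined protocol and SAP*

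**What the plan says.** Section 13 (Statistical Considerations, Aims 1 and 2) gives one analysis for each tracer's regional V_T, a "linear mixed model featuring scan state (baseline and post-alcohol) as within-subject fixed factors, and region as a within-subjects factor". The expected result is stated as: "We hypothesize that the model will identify a significant main effect of scan state". It continues: "Effect sizes of alcohol relative to baseline will also be estimated", and "These values will guide selection of the experimental protocol for Aim 3". Post-alcohol is a single level, and route appears nowhere in the section.

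The design is staged by route. In section 4.1, Aims 1a and 2a give oral alcohol: "This will be done in at least the first 5 subjects". The percent change in V_T is then examined. If it lies within test-retest variability (9-12% for FPEB, under 12% for ABP688) "in subjects achieving the targeted alcohol dose, then we may proceed to Aim 2b", with matching text for Aim 1b. The breakdown of aims lists "Aim 1: 10 moderate drinkers" and the same number for Aim 2. Each subject has a baseline and one alcohol condition per tracer. The third scan allowed per tracer under PET Scans (section 4.4) is for rescheduling.

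The Statement of Purpose says: "This question of route of administration is a critical question in the experimental paradigm optimization, and will be addressed in subaims 1A, 1B, and 2A," and 2B, before Aim 3.

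**The concern.** The design can change route part-way through a tracer, but the model cannot see the change. Each subject receives one route per tracer, so route varies between subjects. Without a route term, the oral and i.v. subjects share one post-alcohol level. The oral subjects in that average are there because their change looked small, since that is what triggers the switch.

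Two things are at stake. The sub-aims are meant to settle the route question, and section 13 contains no analysis that does so. The effect size that guides Aim 3 (30 moderate drinkers and 30 people with AUD) could also describe a mixture of routes rather than the paradigm Aim 3 would use. A tracer that responds to i.v. alcohol could then look weak.

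**Working it through.** **Inputs from the documents.** Ten subjects per tracer; oral in at least the first 5, so at most 5 i.v. after a switch; cut-offs of 9% and 12%. The only dispersion figure is test-retest variability under 12%. For Aims 1 and 2 the plan gives no alpha, power, SD or expected effect, so it has no figure to reproduce.

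**Assumptions.** Two-sided 5%; SD of a subject's percent change 12% (range 9-15%), equal in both routes; one summary region per subject; a 5+5 split; a switch when the mean oral fall is below 9% or below 12%. Ranges below run over those two cut-offs. Effects are percent change in V_T.

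**Step 1: what the route-blind model estimates.**
Pooled effect = (n_oral x oral effect + n_iv x i.v. effect) / 10.
With oral 0 and i.v. -15%:
- 5+5: (0 + 5 x -15)/10 = -7.5%, or 50% of the i.v. effect
- 6+4: -6.0%, or 40%
- 7+3: -4.5%, or 30%

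This step needs no SD.

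**Step 2: allow for the switch rule.** Oral data are followed by i.v. only when the oral fall is small. With m the true oral fall and c the cut-off, z = (c - m)/(SD/√5). The expected oral fall given a switch is m - (SD/√5) x φ(z)/Φ(z).
For m = 0, c = 9, SD = 12: SD/√5 = 5.37, z = 1.68, P(switch) = 0.953. The expected fall is -0.55, so the pooled estimate is -(15 - 0.55)/2 = -7.2%. With c = 12 it is -7.4%.

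**Step 3: power at 5+5, SD 12%, oral 0, i.v. -15%.**
- i.v. contrast with variance pooled across routes (8 df): noncentrality 15/(12/√5) = 2.80, critical value 2.31, power 69%.
- i.v. subjects alone (4 df): same noncentrality, critical value 2.78, power 56%.
- Route-blind test (9 df): the ignored route difference also inflates the variance to about 144 + (10/9) x 7.5² = 206.5, an SD of 14.4. The typical statistic is 7.5/(14.4/√10) = 1.65 against a critical value of 2.26. Simulated power is 25-28%.

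**Step 4: vary the oral effect** (SD 12%; simulated, given a switch).

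| Oral / i.v. effect | P(switch) | Pooled estimate | Power, pooled | Power, i.v. contrast (8 df) |
|---|---|---|---|---|
| 0 / -15% | 95-99% | -7.2 to -7.4% | 25-28% | 69% |
| -5% / -15% | 77-90% | -9.0 to -9.5% | 48-54% | 69% |
| -8% / -15% | 57-77% | -9.7 to -10.4% | 59-67% | 69% |
| -8% / -8% | 57-77% | -6.2 to -6.9% | 29-38% | 26% |

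**Step 5: vary the SD.** With oral 0 and i.v. -15%, power is 39-40% pooled against 90% at SD 9%, and 16-19% against 50% at SD 15%. With oral -8% and i.v. -15% at SD 9%, it is 88-91% against 90%, so the two are level.

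**Step 6: type I error, no effect by either route.** The pooled test holds 5.0%. Deciding on the adopted route (i.v. after a switch, otherwise oral in all 10) gives about 5.0-5.9% over SD 9-15%. The excess arises because oral data stay deciding only when the fall is large.

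**The case against.** The strongest reply is that pooling is never stated. Oral and i.v. are separate sub-aims, the oral subjects are examined on their own at the look, and fitting the section 13 model within each sub-aim would be consistent with the text. That stands as far as it goes: averaging is what the written model implies with all 10 subjects included, and no sentence instructs it. But no sentence specifies separate fits, says what happens to the oral-stage data, or says which route's effect size goes forward.

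The reply is also right that halving is a near-worst case. It needs a zero oral effect, whereas the rule asks only that the change lie within test-retest variability, and the switch is optional. Real oral effects can trigger it, and the loss then shrinks.

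Three stronger readings are tempting, and the documents do not support them:
- A reader might infer that the plan names no deciding effect. It names the main effect of scan state; only a route-specific version is missing.
- A reader might infer a false-positive rate of roughly double from choosing among oral, i.v. and pooled results. That requires analysts to abandon the named main effect, which by itself holds 5.0%.
- A reader might take the 40 moderate drinkers in section 6 as 10 + 10 + 20, proving that no separate i.v. cohort exists. The sum assumes different people in Aims 1 and 2, while the plan hopes to enrol the same ones, and the total is a ceiling. The better support is 10 per aim. Even that does not expressly divide the 10 by route, so 5+5 is an assumption.

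**Conclusion.** The point holds, conditional on a switch and on all 10 subjects of a tracer entering the model as written. The scan-state effect is then a route average. It cannot answer the route question, and it understates the adopted route when oral alcohol has the smaller effect.

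The size depends on the unknown oral effect. At SD 12% and i.v. -15%, the pooled estimate runs from about half the i.v. effect (oral 0) to about two thirds (oral -8%). The power deficit against the i.v. contrast runs from over 40 percentage points to between 2 and 10. With equal effects in both routes, pooling is the more powerful choice. The SD, effects, alpha and split are assumptions. The missing route term is a matter of reading and does not depend on them. If no switch occurs, the issue does not arise.

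This should be corrected before any switch is made. Aims 1 and 2 are for optimising the paradigm and their effect sizes only guide Aim 3, so it is not a fatal flaw.

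**What to change.** In section 13, for any tracer in which the switch occurred:
- Add route (oral or i.v.) and scan state x route to the Aims 1 and 2 model.
- Name scan state within the adopted route as the deciding contrast: i.v. after a switch, otherwise oral in all 10.
- Use that route-specific estimate, with its confidence interval, as the effect size that guides Aim 3.
- Report the other route's estimate and the pooled effect as descriptive.

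Separately, PET Scans in section 4.4 describes only i.v. alcohol for the challenge scans, whereas sections 1 and 4.1 put oral first. These passages must be reconciled.

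The cost is wording and two model terms, with no added subjects or scans. There are four downsides:
- The deciding estimate rests on 5 or fewer i.v. subjects, so its interval is wider.
- Power is lower than with pooling if the routes have equal effects.
- The 69% relies on equal variance across routes; with i.v. subjects alone it is 56%.
- Overall type I error is about 5.0-5.9% rather than 5.0%, which the plan should acknowledge.
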